3.3 Rationale

AL amyloidosis is a variant plasma cell disorder in which clonal bone marrow plasma cells produce immunoglobulin light chains that misfold into fibrils that are deposited in visceral organs, leading to organ dysfunction and failure. Untreated, the disease has a median survival of only about one year. Oral treatment with melphalan and dexamethasone produces improvement in survival, with hematologic remissions and improvement in organ function. Aggressive treatment with high dose intravenous melphalan with autologous stem cell transplantation (HDM/SCT) produces complete hematologic responses (CR) in about 40% of subjects and partial responses in a similar proportion; these are frequently accompanied by stabilization or improvement in organ function. Unfortunately only about half of referred subjects are eligible for HDM/SCT. Furthermore, it has been observed by us as well as other groups that achievement of a hematologic complete response after treatment with oral melphalan and dexamethasone as well as HDM/SCT is associated with improved survival, QOL, and clinical/organ response. Thus, we continue to seek more effective regimens for subjects ineligible for aggressive treatment with HDM/SCT or not achieving a complete hematologic response to HDM/SCT or other modalities.

The advent of novel agents in the treatment of multiple myeloma has changed the therapeutic landscape of plasma cell dyscrasias. Thalidomide has been studied as a single agent and in combination with dexamethasone for the treatment of AL amyloidosis. Unfortunately, thalidomide is poorly tolerated with 50-65% of subjects experiencing grade 3 and 4 toxicities, leading to drug withdrawal in approximately half of the subjects.

We are concluding a phase II study of lenalidomide alone and in combination with dexamethasone for subjects with AL amyloidosis. This study included untreated as well as relapsed subjects after HDM/SCT. Interim analysis of the first 34 subjects suggests achievement of a complete hematologic response CR in ~30% subjects and of partial hematologic response in ~40% subjects, with most responses occurring with the lenalidomide/dexamethasone combination. A variety of toxicities have been observed, including leukopenia, rash, venous thrombosis, and intolerance to the dexamethasone. This report indicated better tolerability than thalidomide, however, 20% of subjects still stopped treatment with lenalidomide due to toxicities. We have extended our study to subjects on dialysis, using attenuated doses, with good preliminary results. A study using lenalidomide

in combination with melphalan and dexamethasone is ongoing; this study is not suitable for subjects with significant prior exposure to alkylator agent.

Pomalidomide (CC4047), a third generation immunomodulatory agent, has shown promising activity in phase II trial in combination with low-dose dexamethasone for relapsed or refractory multiple myeloma as well as AL amyloidosis. Furthermore, responses were seen in 50% of subjects who were refractory to prior IMiD in AL amyloidosis.

Given these promising results of pomalidomide in plasma cell dyscrasia, we propose a study of pomalidomide and low dose dexamethasone in the treatment of subjects with previously treated AL amyloidosis.

4 Study Objectives and Endpoints

4.1 Objectives

4.1.1 Primary objectives

• Determine dose-limiting toxicity (DLT) and the maximal tolerated dose (MTD) of pomalidomide combined with dexamethasone in subjects with previously- treated light-chain (AL)-amyloidosis

4.1.2 Secondary objectives

- Determine the following at the MTD:
 - Hematological complete (CR) very good partial (VGPR) and partial (PR) rates
 - duration of response
 - organ response
 - Time-to-event
 - Survival

4.1.3 Exploratory study objectives

• To investigate the relationship of changes in the levels of the biomarkers BNP and troponin I to frequency of specific adverse events and the occurrence of DLT

4.2 Endpoints

4.2.1 Primary Endpoint

• Maximum tolerated dose

4.2.2 Secondary Endpoints

- Hematological CR and PR
- Response-duration
- Organ response
- Time-to-event
- Survival

4.2.3 Exploratory study Endpoint

• The relationship of changes in the levels of the biomarkers BNP and troponin I to frequency of specific adverse events and the occurrence of DLT

5 Investigational Plan

5.1 Overall design

STUDY DESIGN:

Phase I/II dose-escalation study of pomalidomide and dexamethasone in persons with previously-treated AL-amyloidosis. During the Phase I portion the MTD will be determined based on DLT in the first cycle. At the MTD an expanded cohort of 12 subjects will be evaluated to estimate efficacy.

The study includes a screening period, a treatment (dose escalation) period, and a follow-up period for survival. After giving written informed consent, subjects will be evaluated for eligibility for enrollment in the study and baseline evaluations will be performed. Subjects who satisfy all inclusion and exclusion criteria will begin study drug treatment with dose escalation. Standard dose escalation rules will be used.

Subjects will be monitored every cycle for safety, hematological status, and organ function during therapy or until the occurrence of progressive disease (PD).

Treatment Group Assignments and Subject Replacement

This is a dose-escalation study and dose escalation will proceed through 3 dose-levels according to standard rules in which dose levels are started sequentially after complete evaluation of the occurrence of DLT. Based on the dose escalation scheme, as many as 30 subjects could be enrolled in the study. Subjects who discontinue pomalidomide for reasons other than DLT before completing at least 2 treatment cycles are to be replaced.

Subpopulations

An additional 12 subjects will be enrolled in an expanded cohort for analysis of efficacy at each schedule studied.

Subjects in this cohort will be treated at the dose defined as the MTD for that schedule.

Pomalidomide

Schema:

Phase I:

Pomalidomide 2 mg/day D1-21 – dose escalation to 4 mg/day by 1 mg units* Dexamethasone 10-20 mg D1, 8, 15, 22

* Pomalidomide dosing for Phase I cohorts 1 and 2 given on days 1-28 of a 28-day cycle and changed to Days 1-21 of a 28 day cycle with Cohort 3.

This cycle will be repeated every 28 days.

Subjects will take aspirin 325 mg/day to prevent venous thrombosis whilst on-study. A proton pump inhibitor will be used for GI prophylaxis.

Phase II:

Pomalidomide [MTD] mg/day D1-21 Dexamethasone 10-20 mg D1, 8, 15, 22

This cycle will be repeated every 28 days.

Subjects will take aspirin 325 mg/day for prophylaxis against venous thrombosis while on study. A proton pump inhibitor will be used for GI prophylaxis.

Subjects will have a toxicity evaluation, physical examination, and blood work performed according to schedule 2 while on therapy before each cycle. All subjects will return to Boston Medical Center prior to each of the first 3 cycles of therapy. The screening evaluation covers this requirement for cycle 1. A full disease evaluation will be performed at Boston Medical Center after every three cycles to determine response to treatment. Following cycle 3, subjects that are stable, may return every three months. Only one month of study drug may be supplied at a time for each cycle. A complete study calendar can be found in Section 2. Interim CBC may be performed locally. All results will be transmitted to the Clinical Trials Office for review.

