5.4.2 Dosing regimen

The initial planned dose of pomalidomide for investigation is 2 mg/day, orally on days 1 - 21 (28 day cycle).* Dosing will be in the evening at approximately the same time each day,

either 2 hours before or 2 hours after food ingestion. Participants will be instructed to avoid smoking, as smoking can decrease the efficacy of pomalidomide. Only enough pomalidomide for one cycle of therapy will be supplied to the subject each cycle.

* Pomalidomide dosing for Phase I cohorts 1 and 2 given on days 1-28 of a 28-day cycle and changed to Days 1-21 of a 28 day cycle with Cohort 3.

The planned dose levels of Pomalidomide are presented below in Table 15-1 table.

		Enrollment (Number of Subjects)					
Dose Group	Pomalidomide Dose (mg/dose)	Initial	Expanded at MTD ^a				
1	2	3 ^b	3				
2	3	3	3	12			
3	4	3	3				

Table 15-1 Planned Study Drug Doses

a. Twelve additional subjects are to be enrolled in an expanded cohort for analysis of efficacy and treated at the MTD for each dosing schedule.

b. If the first 2 subjects enrolled experience DLT then this cohort is closed and further subjects will be evaluated at 1mg/day dose and the cohort expanded at that dose.

The dose escalation rules will follow the standard Fibonacci method.

Dose escalation algorithm

At least 3 subjects are to be enrolled in each dose group, beginning with the 2 mg/dose. Within each dose group, 3 subjects are to complete at least 2 treatment cycles. It is noted that if the first 2 subjects in the first cohort develop DLT, then the cohort at the 1 mg/dose dose will be defined as the MTD.

Dose escalation within a cohort is not allowed.

- If after all 3 subjects complete 1 treatment cycle:
 - No subject experiences DLT, then enrollment at the next planned dose level may commence.
 - One subject experiences DLT, then 3 additional subjects are to be enrolled at the current dose level.
 - If 1 of 6 subjects experiences DLT, then enrollment at the next planned dose level may commence.
 - If 2 or more of 6 subjects experience DLT, then the previous dose is declared the MTD.

Two or more subjects experience DLT, then the previous dose is declared the MTD.

- Dose escalation continues through the 3 dose levels in order to define the MTD based on the occurrence of DLT in the first cycle. Definitions of DLT and MTD are as follows:

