9.2 Data Monitoring Committee

Toxicity and accrual monitoring will be performed on a routine basis by the study investigators as well as the multidisciplinary members of the Amyloid Treatment and Research Program at Boston University, which has over 40 years' experience in the treatment of AL amyloidosis. Subjects will undergo toxicity assessment, performance status assessment and laboratory tests before beginning each new cycle. Response assessment will be conducted every three cycles. The clinical status and laboratory reports of the study participants will be reviewed routinely by the co-investigators at the weekly meetings of the Stem Cell Transplant Program and reviewed by the Amyloid Program at weekly meetings. Dose modifications/interruptions or discontinuation will be implemented according to Section 5.5.

In addition, the BMC Cancer Center's Internal Data and Safety Monitoring Committee (DSMC) will review the protocol, and will determine review frequency based on level of risk. The protocol will be reviewed at least annually by the DSMC. Please see full DSMB Charter in Appendix 4.

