10.3 Statistical Methodology

Determination of Sample Size

Based on the dose escalation scheme, as many as 30 subjects may be enrolled in this study.

The number of subjects enrolled will depend on the outcome of the actual dose escalation process. The dose-escalation phase consists of 3 cohorts, each with 2 to 6 subjects enrolled depending on when DLT occurs. Therefore, a minimum of 2 and a maximum of 18 subjects will be enrolled in this phase.

An additional 12 subjects will be enrolled in an expanded cohort for efficacy at each schedule. Therefore, an additional 12 subjects could potentially be enrolled.

It is expected that approximately 30 patients will be enrolled in the phase I/II portions of this study. The endpoints measured in the protocol will be overall response rate (ORR) determined by either CR, VGPR or PR and response of one or more organs. It is estimated by the principle investigator's approximate frequency of response in 18 patients (6 patients will be dosed at the MTD during the phase I portion of this trial plus the additional 12 patients at this MTD dose during the phase II portion). Using the adjusted Wald's confidence interval for the proportion and the corresponding point estimates for hypothetical data, it is expected that if 6 out of 18 have ORR then the estimated response rate would be 35.57% with a 90% confidence interval between 18.21% and 52.81% with similar estimates for organ response.

Randomization and Stratification This is not a randomized study.

Populations for Analysis

The safety population will include all subjects who received at least 1 dose of study drug.

The additional 12 subjects enrolled in the expanded cohort for efficacy will comprise the efficacy population.

Procedures for Handling Missing, Unused, and Spurious Data

No imputation of values for missing data will be performed. Standard clinical monitoring and data management practices will be used to ensure the integrity of data.

General Methodology

In general, summary tabulations will be presented by dose group showing the number of observations, mean, standard deviation, median, minimum, and maximum for continuous variables, and the number and percent (calculated using non-missing values) per category for categorical data.

Safety Analysis

• Determination of MTD

The determination of MTD will be achieved by the results of a deterministic algorithm; thus, statistical hypothesis testing is not intended.

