The evaluation of MTD will be based on data from subjects who receive pomalidomide and whose data are interpretable in the context of study drug-specific toxicity (ie, subjects should have had sufficient safety assessments performed to determine whether DLT occurred and should not have received alternate antineoplastic therapies through cycle 1). Subjects who are withdrawn from the study for reasons other than DLT before completing cycle 1 and are replaced consequently will not be included in the analysis of MTD. Subjects will be analyzed according to the dose actually received.

Pharmacokinetics/Pharmacodynamics Not applicable.

Efficacy Analysis

The efficacy analysis will be based on confirmed hematological response and confirmed organ response. The analysis of response data at the MTD will be descriptive, consisting of 2-sided 90% confidence intervals.

Additional analyses of efficacy data at the MTD will consist of evaluations of time to hematologic response, duration of hematologic response, and time to worsening of hematologic and/or organ function. These analyses will also be descriptive in nature.

Analysis of the rates of responders for each of the other dose levels will also be presented, without calculation of confidence intervals.

Exploratory Analysis

An exploratory analysis will be conducted to investigate the relationship of changes in the levels of the biomarkers brain natriuretic peptide (BNP) and troponin I to the frequency of specific AEs and the occurrence of DLT. Additionally, the benefit, if any, of using these measures in addition to routine monitoring by ECG and echocardiogram will be explored. The frequency of conversion in immunofixation results from positive to negative will be explored and the disappearance of free light chain. Efficacy at additional doses may be explored for potential use in future Phase II clinical trials.

Interim Analysis

Interim analyses will be performed following each cohort during the Phase I portion of the study. No interim analysis is planned for the Phase II portion.

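### Response percentages on non-missing values let subjects who die, withdraw or are lost before any assessable result leave the denominator, which can bias the descriptive response rate slightly upward

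*Combined protocol and SAP*

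**What the plan says.** - **Denominator.** The general methodology in 10.3 reports categorical data as "the number and percent (calculated using non-missing values) per category for categorical data". The missing-data paragraph adds: "No imputation of values for missing data will be performed". No section assigns a response category to a subject who was never assessed.
- **Efficacy population.** Section 10.3 states: "The additional 12 subjects enrolled in the expanded cohort for efficacy will comprise the efficacy population". The sample-size paragraph of the same section instead uses 18 subjects, 6 from Phase I at the MTD plus the 12.
- **Timing of assessment.** Section 5.1 states: "A full disease evaluation will be performed at Boston Medical Center after every three cycles to determine response to treatment". Section 9.2 agrees: "Response assessment will be conducted every three cycles". In the Section 2 schedule, free light chains are repeated on day 1 of cycles 2 and 3. Immunofixation and 24-hour urine protein are first repeated at cycle 4.
- **Replacement.** The synopsis and 5.1 state: "Subjects who discontinue pomalidomide for reasons other than DLT before completing at least 2 treatment cycles are to be replaced". The escalation algorithm in 5.4.2 has a matching requirement: "Within each dose group, 3 subjects are to complete at least 2 treatment cycles". The MTD paragraph of 10.3, which governs the MTD analysis only, uses a different cut-off: "Subjects who are withdrawn from the study for reasons other than DLT before completing cycle 1 and are replaced consequently will not be included".

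**The concern.** In a single-arm study the response rate has no control to absorb a selective denominator. A subject who dies or is lost before the first on-treatment result is unlikely to have been a responder. Leaving such subjects out raises the rate, and the 90% confidence interval does not show it, because it reflects sampling error only. Section 10.1 compares the result informally with lenalidomide plus dexamethasone, so an upward shift would flatter that comparison.

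The replacement rule has no exception for death or progression, and its two-cycle cut-off falls before the first full evaluation. If replaced subjects at the MTD are not counted, it acts in the same direction. Because the text allows either denominator, the choice could also be made after results are known.

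**Working it through.** **1. The plan's own figure.** Section 10.3 gives 35.57% (90% CI 18.21% to 52.81%) for 6 of 18, by adjusted Wald. With z = 1.645 and z² = 2.706:

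- n~ = 18 + 2.706 = 20.706
- p~ = (6 + 1.353)/20.706 = 35.51%
- half-width = 1.645 × √(0.3551 × 0.6449/20.706) = 17.30 points
- interval 18.21% to 52.81%, width 34.60 points

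Both limits reproduce. The printed point estimate is 0.06 above the computed one. The raw proportion, 6/18 = 33.3%, is the base rate below.

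**2. What can be classified, and when.** Section 7.1 defines VGPR and PR by dFLC alone, so a subject with the cycle 2 light-chain result can be given a hematologic category. For hematologic response, only loss before about day 28 leaves nothing to classify. For measures first repeated at cycle 4, such as 24-hour urine protein for kidney response, the exposed period runs to about day 84.

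**3. Deaths alone under the non-missing rule.** Section 3.2 quotes 77% one-year overall survival in an earlier pomalidomide study in previously treated AL amyloidosis. Two assumptions are made: survival is exponential, and those who die would be non-responders. With d the share dying, the reported rate is p/(1 − d).

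| Gap ends | d | Reported rate | Bias |
|---|---|---|---|
| Day 28 | 1 − 0.77^(28/365.25) = 1.98% | 33.33/0.9802 = 34.01% | 0.7 point |
| Day 84 | 1 − 0.77^(84/365.25) = 5.83% | 33.33/0.9417 = 35.40% | 2.1 points |

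These biases depend on p and d only, so they are the same for 12 and 18 subjects.

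**4. Per subject lost.** The documents give no early withdrawal or loss rate for this trial, so the remaining effect is shown by head count, assuming that those lost are non-responders.

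| Lost | 6 responders of 18 | 4 responders of 12 |
|---|---|---|
| 1 | 6/17 = 35.3% (+2.0) | 4/11 = 36.4% (+3.0) |
| 2 | 6/16 = 37.5% (+4.2) | 4/10 = 40.0% (+6.7) |

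**5. Replacement, only if it applies at the MTD and replaced subjects are not counted.** With one non-responder replaced, a reported 6/18 (33.3%) is 6/19 = 31.6% of all treated, an overstatement of 1.8 points. A reported 4/12 is 4/13 = 30.8%, an overstatement of 2.6 points. If the rule covers escalation only and the efficacy population is the 12 expansion subjects, the overstatement is zero.

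**The case against.** The best defence is that exclusion is inferred from silence. The efficacy population is defined by enrolment, with no evaluability condition. The non-missing rule is introduced as a general convention for summary tables, and the Efficacy Analysis paragraph does not repeat it. That paragraph requires confirmed responses, so a subject without one could be read as a non-responder, and the stable-disease definition in 7.1 might absorb unassessed subjects. This shows that the plan is ambiguous, but it does not supply the missing rule. The one stated rule on percentages points to exclusion.

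Follow-up narrows the gap. Section 5.8 follows everyone who stops treatment every three months, and progression is a defined category, so documented progression is not missing. Follow-up cannot help for deaths or losses. It is also uncertain for others, because 5.5.3 removes from the study those who permanently stop pomalidomide.

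Four stronger readings are tempting but not supported:

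- **Replaced subjects are excluded from the response analysis.** The only explicit exclusion concerns the MTD. The replacement rule sits in the dose-escalation paragraph, before the expansion cohort is introduced, and may not reach that cohort.
- **The response rate is the only efficacy estimate.** Organ response, response duration, time-to-event and survival are also planned (4.1.2, 4.2.2, 10.3), and survival would show early deaths.
- **The 56% one-year progression-free survival should set the size.** That would treat documented progressors as missing.
- **The 20% who stopped lenalidomide for toxicity (3.3) gives the early loss rate.** That figure covers a whole course of treatment and does not describe loss before assessment.

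The direction is also not certain in every case. A subject with an early light-chain response who then stops and is replaced would lower the rate.

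**Conclusion.** The concern holds as a minor defect. As written, 10.3 lets subjects without an assessable result leave the response denominator, and no non-responder rule offsets this. The documents do not fix the size. The 0.7-point figure for hematologic response and the 2.1-point upper figure for measures first repeated at cycle 4 count deaths only. They rest on exponential survival at the rate quoted in 3.2, a 33.3% response rate, and no response among those lost. Withdrawals and losses would add to them, and the head-count figures are illustrations because no loss rate is given. Any effect of replacement is conditional and may be zero.

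Response is a secondary, descriptive endpoint, and these shifts are small beside its interval. The MTD has its own evaluability rule and does not depend on the response denominator.

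**What to change.** In 10.3, for hematologic and organ response:

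- Replace the non-missing denominator with all subjects whose assigned starting dose and schedule was the MTD and who received at least one dose. Subjects from lower cohorts who later move up under 5.4.1 are then not included. For organ response, restrict to those with an evaluable involved organ at baseline, since 7.2 makes nerve-only or gastrointestinal-only involvement indeterminable.
- Count subjects with no post-baseline assessment as non-responders.
- Keep any replaced subjects in, and report how many were replaced and why.
- Show the 12-subject expansion cohort alone, and an evaluable-only rate as a sensitivity analysis.

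Reconcile the two-cycle replacement wording (synopsis, 5.1, 5.4.2) with the cycle-1 basis for DLT and MTD evaluation (5.4.1, 10.3), and state whether replacement applies to the expansion cohort.

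The cost is a wording change with no new data collection. The reported rate may be slightly lower, and one sensitivity row is added.

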5.4 Drug Administration

5.4.1 Treatment assignments

The Phase I portion of the study will be aimed at determining the safety profile and the MTD of Pomalidomide. A 3+3 dose escalation scheme will be implemented. Subjects will receive escalating doses of Pomalidomide orally on D1-21 in a 28-day cycle* in the absence of disease progression or unacceptable toxicity. DLTs will be assessed in Cycle 1 only. Dose escalation of Pomalidomide will continue until MTD has been identified or a maximum planned dose (4 mg/day D1-21) is determined to be safe.

* Pomalidomide dosing for Phase I cohorts 1 and 2 given on days 1-28 of a 28-day cycle and changed to Days 1-21 of a 28 day cycle with Cohort 3.

The Phase II portion of the study will begin after determination of the MTD and evaluation of the safety profile at the MTD in at least 6 subjects. The dose for administration will be informed by the results of the Phase I portion of the study. In the Phase II, eligible subjects will receive Pomalidomide at the MTD or the maximum planned dose from D1-21.

Once the MTD is defined during Phase I, patients currently receiving treatment may discuss the option with the treating investigator to continue on their current dose, or increase to the MTD, if they have not achieved a complete response.

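### Does replacing two-cycle leavers while judging DLT on Cycle 1 leave the MTD decision open?

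*Combined protocol and SAP*

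**What the plan says.** Two windows are in use.

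- **Two cycles, for replacement and exposure.** The synopsis and Section 5.1 state: "Subjects who discontinue pomalidomide for reasons other than DLT before completing at least 2 treatment cycles are to be replaced". Section 5.4.2 adds: "Within each dose group, 3 subjects are to complete at least 2 treatment cycles".
- **One cycle, for the dose decision.** Section 5.4.1: "DLTs will be assessed in Cycle 1 only". The algorithm in Section 5.4.2 begins "If after all 3 subjects complete 1 treatment cycle". Section 10.3 removes from the MTD analysis only those who withdraw for non-DLT reasons before finishing Cycle 1.

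The consequences in Section 5.4.2 depend on a count of DLTs: "One subject experiences DLT, then 3 additional subjects are to be enrolled at the current dose level" and "Two or more subjects experience DLT, then the previous dose is declared the MTD". The MTD is defined there, and again in Section 10.2, as a level with at most one DLT in six subjects. Under Section 5.5.1, a Cycle 1 DLT must bear on escalation and expansion and is tallied for the cohort in which it happened; later-cycle DLTs may be considered at the investigators' discretion. Section 5.1 adds that "dose levels are started sequentially after complete evaluation of the occurrence of DLT", and Section 10.5.1 holds accrual during each Phase I look. Section 10.3 gives a maximum of 18 subjects in escalation and 30 overall.

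**The concern.** A subject who completes Cycle 1 without DLT and stops in Cycle 2 has already given the result that the dose decision needs. The subject stays in the MTD count, yet must be replaced. The cohort then has 4 or 7 subjects, while the algorithm is written for 3 and 6.

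Timing adds to this. For the last subject enrolled in a cohort, Cycle 2 starts only after the look. A replacement's 28-day Cycle 1 therefore ends at least 28 days after the level may have been cleared at 0/3 or 1/6 and the next one opened. If the replacement has a DLT, the cohort stands at 1/4 or 2/7. Nothing states whether a cleared level re-opens. Section 10.3 presents MTD determination as algorithmic, so a choice made after the event is known would weaken that claim for the primary endpoint. The enrolment maxima also leave no room for replacements.

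**Working it through.** **1. The plan's own maxima.** 3 cohorts × 6 = 18, and 18 + 12 = 30. Both reproduce, with no allowance for replacements: one on the fullest path gives 19 and 31.

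**2. What the text decides about a replacement's DLT.** Take a cohort cleared with one Cycle 2 leaver and one replacement. Let p be the DLT rate (not in the documents; 0.20 and 0.30 assumed). P(clear at 0/3) = (1−p)³ = 0.512 and 0.343. P(clear at 1/6) = 3p(1−p)⁵ = 0.197 and 0.151. The chance that the level stays cleared is then:

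| Treatment of the replacement | Formula | p = 0.20 | p = 0.30 |
|---|---|---|---|
| Ignored | (1−p)³ + 3p(1−p)⁵ | 0.709 | 0.494 |
| Added (1/4 filled to 6; 2/7 fails) | (1−p)³[(1−p) + p(1−p)²] + 3p(1−p)⁶ | 0.632 | 0.396 |
| Substituted (1/3, three more; 2/6 fails) | (1−p)³[(1−p) + p(1−p)³] + 3p(1−p)⁶ | 0.619 | 0.381 |

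The large gap lies between ignoring the DLT and counting it, and Section 5.5.1 rules out ignoring it. The two ways of counting differ by 0.632 − 0.619 = 0.013 and 0.396 − 0.381 = 0.015.

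**3. How often a leaver occurs.** The documents give no Cycle 2 loss rate. As a proxy, the one-year progression-free survival of 56% in the earlier pomalidomide amyloidosis study (Section 3.2) gives q = 1 − 0.56^(28/365.25) = 0.0435 per cycle. The proxy is weak: it counts progression and death, and here "A full disease evaluation will be performed at Boston Medical Center after every three cycles".

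**4. Who can leave after the look.**
- *Six-subject look:* the second trio starts after the first trio has finished Cycle 1, so the first trio's Cycle 2 is over by then.
- *Three-subject look:* 30 subjects in about 24 months is one per 24 days or so. The first subject's Cycle 2 ends on day 56, before a look on day 24 + 24 + 28 = 76. For the second subject about 24/28, or 86%, of Cycle 2 falls before it.

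In practice this leaves mainly the last-enrolled subject.

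**5. Per cohort, last-enrolled subject only.** P(replacement DLT after clearance) = qp × P(clear):
- p = 0.20: 0.0087 × 0.709 = 0.0062
- p = 0.30: 0.0130 × 0.494 = 0.0064

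If every DLT-free subject could leave after the look, qp is replaced by 1 − (1−qp)³ at 0/3 and 1 − (1−qp)⁵ at 1/6:
- p = 0.20: 0.512 × 0.026 + 0.197 × 0.043 = 0.022
- p = 0.30: 0.343 × 0.039 + 0.151 × 0.064 = 0.023

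**6. Whole escalation, by simulation.** Three levels were simulated with DLT rates of 20% throughout, 30% throughout, or 10/20/30%. The replacement's DLT is always counted, and the final MTD needs at least six subjects with at most one DLT. The comparison is re-opening the level against letting the clearance stand.

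| Who may leave after the look | Trials with such a DLT | Declared MTD differs |
|---|---|---|
| Last-enrolled only | about 1.1–1.4% | about 0.25–0.5% |
| Every DLT-free subject (near upper bound) | about 4–5% | about 1.0–1.7% |

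The last column moves by a few tenths of a point with the coding of the fill to six.

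**7. Exceeding 18.** On the path with 1/6 at every level there are 15 DLT-free subjects, and 1 − (1 − 0.0435)¹⁵ = 0.49. That path has probability 0.197³ = 0.008 or 0.151³ = 0.003, so the 49% describes a rare route.

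**The case for a change.** The best case for a change is that the mismatch is real and cheap to remove. Section 5.1's complete-evaluation condition is met at the look, because DLT is a Cycle 1 matter. The accrual hold covers the look and not what follows it. The discretion in Section 5.5.1 concerns later-cycle DLTs, not a replacement's Cycle 1 DLT. The requirement in Section 5.4.1 for at least six subjects at the MTD re-checks the final dose, not a lower level already passed. A few sentences would close the gap before anyone has seen an event.

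Much of this stands as description: no sentence deals with a late replacement DLT once the next level is open. It does not show that the plan lacks direction. The DLT counts for its cohort. The Section 5.4.2 branches, read by count, call for more subjects at 1/4 and for the previous dose at 2/7, and the MTD definition agrees with the latter. Letting a clearance stand against a second DLT has little support in the text.

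Narrowing replacement to Cycle 1 would also have a cost. Section 5.4.2 asks for three two-cycle completers per level, and Section 5.5.1 lets later-cycle toxicity inform escalation. Some of that exposure would be lost.

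**Conclusion.** No change follows. The two windows differ but can be applied together: the Cycle 2 leaver keeps the Cycle 1 result, the replacement supplies the second-cycle exposure, and the replacement's own Cycle 1 DLT is counted. The one unwritten detail is how this applies when subjects are already at the next level. Sections 5.4.2 and 5.5.1 give the investigators enough to handle it sensibly.

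Under the assumed 4.3% loss and DLT rates of 10 to 30%, it would alter the declared MTD in roughly 0.25 to 0.5% of trials, with 1.0 to 1.7% near an upper bound. Those figures rest on a weak proxy for loss and treat a standing clearance as a live alternative, which the text hardly supports.

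The two-cycle window is a fair trade-off. The maxima of 18 and 30 exclude replacements of any kind, including ordinary Cycle 1 ones. Sections 5.2 and 10.3 also describe the total as approximate, so a note to that effect would change no result.
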